## **6) Procedures**

Data collected from children and families includes process data about interactions with families, family survey data, and administrative data about children's medical and educational services use. Process data about interactions with families will be collected by family navigators (who are part of the research team) using the Care Coordination Management Tool and the Navigator Fidelity Checklist, which are study tools adapted from existing measures. Only members of the study team will have access to these data, and these data will be securely kept on the OHSU Sharepoint secure cloud storage throughout the study. These data are collected for the purposes of evaluating this research project.

Survey data from families will be collected in both study arms primarily via a mailed and/or online survey. The survey will be sent upon enrollment and 6 months after enrollment in Autism ALERT or the comparison intervention. Prior to the 6 month post-enrollment survey, a letter will be sent to families informing them of the upcoming survey and the \$50 incentive for completion. A \$50 cash or gift card incentive will be provided for survey completion. The survey will initially be sent 3 times via a secure RedCap link. Then non-responders will be contacted via telephone. Subjects who do not respond to either email or telephone will be sent a survey mailing with a \$5 Dutch Bros coffee card. The survey will be marked with a study number only and will contain no personal identifiers. The study team will have a separate locked document that has the key linking study ID to personal information (see below). Completed surveys will be mailed back to the study team in an envelope and entered into a secure database behind the OHSU firewall. Original copies will be stored in a locked file cabinet in the study team area.

For the expansion, survey data from families will be collected primarily via a mailed and/or online survey. The survey will be sent upon enrollment and 6 months after enrollment in Autism ALERT. Prior to the 6 month post-enrollment survey, a letter will be sent to families

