After consent, secure emails may be transmitted between the family navigator and the PCP, which may contain family information. These emails will be sent via encrypted email using the OHSU Secure Mailbox. This technology requires outside users to log into a website behind the OHSU firewall to send/receive the encrypted email, which minimizes the risk of privacy breach. Secure messages also automatically expire 30 days after creation and are removed from the Secure Mailbox server. Autism ALERT will also have a PCP interface in which PCPs can contact the study team and monitor the status of their patients. This interface will be part of OHSU's RedCap database and thus will also be hosted behind OHSU's firewall. It will require a unique user ID and password, which the study team will assign to each PCP. Each PCP will only be allowed to view his/her own patients on the secure website.

We will also survey providers about intervention fidelity, feasibility and acceptability. Survey data on providers will be collected via a mixed mode (in-person, email, mail, fax) survey, upon enrollment, at the end of subject enrollment (about patient portal use only) and at the end of the study intervention period. The survey will be sent to all providers whose clinics participated in the study, whether or not they were assigned to the study intervention or actually used Autism ALERT. Surveys will initially be sent to providers in person or via an email link, which will connect to a secure RedCap server. The survey will require entry of a study number only and will contain no individual identifiers. Non-responders, identified by a locked

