## **8) Data Analysis**

Process data from CCMT and Navigator Fidelity Checklist will be used to calculate contact attempts, time to first contact, total time spent per family, and counts of specific navigator activities. Families who complete all calls will be compared to those who broke off contact, and specific points of participant drop-off will be calculated. We will assess whether specific intervention activities varied by family demographic characteristic and clinic site, to assess variability in acceptability, using bivariate analyses. Family survey data will also be used to assess feasibility and acceptability. Initial analyses will focus on families who participated in ALERT, assessing experience of care and improvement suggestions. Next, post-intervention family experience will be compared in intervention vs. control clinics using bivariate analyses with an intention-to-treat approach. We will also examine variation in experience outcomes overall, and by study arm, by demographic characteristics, in order to assess whether the intervention was appropriate for diverse families, and to target improvements. Parent responses to open-ended items will be assessed via conventional content analysis. Using the parent interviews, we will also qualitatively assess families' feelings towards the evaluation process, and for the intervention arm we will also be looking at experiences with family navigators.

PCP process data will be used in a similar fashion. PCP/Navigator interactions will be descriptively characterized, using the PCP-Navigator Con-tact log and use of the PCP Website. PCP survey data will be used to characterize PCPs' post-intervention experiences. PCPs' overall experiences will be compared in both arms using bivariate testing, and open-ended questions will be coded.

We will refine our mechanism hypotheses and measurement by examining change in family-and provider-reported outcomes (e.g., stress, empowerment) pre-and post-intervention, in both study arms, primarily using descriptive and bivariate tests. Exploratory analyses will assess whether mechanism outcomes differ by family race/ethnicity, English proficiency, or insurance type, both overall and by study arm, using bivariate or limited multivariable regression analyses. This will allow us to gather valuable descriptive data on variation in engagement of target mechanisms, which might allow for individualized messaging in future research.

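### The pilot compares family experience between arms on the 6-month score alone; for items also asked at enrolment, adjusting for that score would give a more precise estimate

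*Protocol*

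**What the plan says.** Protocol Section 8 sets the family comparison: "Next, post-intervention family experience will be compared in intervention vs. control clinics using bivariate analyses with an intention-to-treat approach". That fixes the time point (after the intervention) and the type of analysis (bivariate, so outcome against arm with no covariate).

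On data collection, Section 6 says of families: "The survey will be sent upon enrollment and 6 months after enrollment in Autism ALERT or the comparison intervention". It speaks of one survey and two occasions, in both arms.

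For providers, Section 8 says "PCP survey data will be used to characterize PCPs' post-intervention experiences" and then "PCPs' overall experiences will be compared in both arms using bivariate testing, and open-ended questions will be coded". Section 6 introduces the provider survey with "We will also survey providers about intervention fidelity, feasibility and acceptability" and times it "upon enrollment, at the end of subject enrollment (about patient portal use only) and at the end of the study intervention period". Only the middle wave is marked as restricted in content.

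Section 8 uses before-and-after data for the mechanism outcomes, with stress and empowerment as its examples, and examines change in both arms. It gives no such treatment to experience.

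Section 4 (Study Design) assigns three clinics to each arm by randomisation, stratified for size and urbanicity, and says feasibility and acceptability are assessed in the intervention clinics. Section 5a plans 25 families and 15 providers per arm. The later expansion has no control arm, so everything here concerns the two-arm pilot.

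**The concern.** A family's rating of its care at 6 months depends partly on how it rated care at the start. With three clinics and about 25 families per arm, the arms can easily differ at the start by chance, and stratifying six clinics on size and urbanicity does little to balance prior experience of care. A comparison of follow-up scores alone carries part of that chance difference into the ALERT-versus-control estimate and gives a wider interval than the collected data may allow.

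The protocol says the pilot is deliberately not powered for significance, but it also says the estimates will supply effect sizes and inform the next trial's sample size. For that purpose precision is what counts. Because the contrast spans both arms, its items cannot be specific to the navigator, so at least some could be asked meaningfully at enrolment.

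**Working it through.** The protocol gives no SD, effect size, power, intracluster correlation (ICC) or enrolment-to-follow-up correlation, so it has no figure of its own to reproduce beyond the counts: 20 + 25 + 25 = 70 dyads and 15 + 15 = 30 providers (Section 5a).

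**Inputs from the protocol:** n = 25 families per arm; 15 PCPs per arm; 3 clinics per arm, so m = 25/3 = 8.3 families per clinic.

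**Assumed, not in the protocol:** correlation rho = 0.3, 0.5 or 0.7; ICC = 0 or 0.05; an experience score that exists at both times.

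**1. Post-only comparison, families, ICC 0.** SE = sqrt(2/25) = 0.283 SD. The 95% half-width is 1.96 × 0.283 = 0.55 SD.

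**2. Adjusted for the enrolment score.** The SE is multiplied by sqrt(1 − rho²):

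| rho | variance removed (rho²) | SE | half-width | 25 per arm acts like 25/(1 − rho²) |
|---|---|---|---|---|
| 0.3 | 9% | 0.270 | 0.53 | 27 |
| 0.5 | 25% | 0.245 | 0.48 | 33 |
| 0.7 | 49% | 0.202 | 0.40 | 49 |

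**3. With within-clinic correlation.** The design effect is 1 + (8.3 − 1) × 0.05 = 1.37, so the post-only half-width is 1.96 × sqrt(2 × 1.37/25) = 0.65 SD. Adjusted, it is 0.62, 0.56 or 0.46 SD. This assumes the enrolment score explains the same share of variation between clinics as within them.

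**4. Few clusters.** With 3 + 3 − 2 = 4 degrees of freedom the multiplier is 2.776 instead of 1.96. Even at ICC 0 the post-only half-width is then 2.776 × 0.283 = 0.79 SD. Multiplying 0.785 by 0.954, 0.866 or 0.714 gives 0.75, 0.68 or 0.56 SD. The proportional gain is unchanged, but an interval that respects clinic can still be wider than the naive 0.55. An exact permutation test of 3 against 3 clinics cannot give a two-sided p below 2/20 = 0.10, so estimates with intervals are more useful here than tests.

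**5. Chance difference at the start.** Its SD is the SE in step 1: 0.28 SD at ICC 0, or 0.33 SD at ICC 0.05. A fraction rho passes into the post-only contrast. A starting difference of 0.3 SD would contribute 0.09, 0.15 or 0.21 SD.

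**6. Why not a change score.** Its variance relative to post-only is 2(1 − rho) = 1.4, 1.0 or 0.6. It is worse than post-only below rho = 0.5, whereas adjustment does not lose in this way.

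**7. PCPs, 15 per arm, ICC 0.** The half-width is 1.96 × sqrt(2/15) = 0.72 SD post-only, and 0.68, 0.62 or 0.51 SD adjusted. Fifteen is the planning figure; Section 6 later mentions 41 participating pediatricians.

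**The case against.** The strongest objection is that no part of the protocol says experience items are asked at enrolment. Section 8 separates post-intervention experience from outcomes examined before and after, which may simply mean that experience is measured only afterwards. A reader might infer from the single family survey in Section 6 that an identical questionnaire is used twice and that a matching baseline is being discarded. The text makes this plausible but does not establish it, so the recommendation has to be limited to items asked at both times.

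A reader might also infer that a primary outcome is biased. The protocol does not support that. Section 4 places the acceptability assessment in intervention clinics, and Section 8 takes up ALERT families first and the arm comparison second, so the contrast is supporting evidence. With randomised clinics, a chance difference at the start is random error, large here but not systematic.

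For PCPs the reading is weaker still. The sentence on comparing arms refers to overall experience; that it means follow-up only is inferred from the sentence before it. Experience of the intervention's feasibility or acceptability cannot be rated before the intervention. Section 5e (Recruitment Methods) also has the initial provider surveys handed out at the training session, so they may not precede the training content.

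Finally, choice of covariates is often left to a statistical analysis plan, which is not at hand. That would answer a protocol that was silent, but Section 8 fixes the family comparison as post-intervention and bivariate.

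**Conclusion.** The point holds in conditional form and mainly for families. The protocol commits the arm comparison of family experience to the follow-up score without adjustment, while describing a survey that appears to supply an enrolment score. Where an item is asked at both times, adjusting for it reduces the variance by 9%, 25% or 49% at an assumed correlation of 0.3, 0.5 or 0.7. At the low end the benefit is slight (0.55 to 0.53 SD); at the middle and upper values it is worth having. For items not asked at enrolment there is no gain. Any interval must also reflect the six clinics, which the enrolment score alone does not achieve. The PCP comparison follows only if comparable items were answered before training content was delivered.

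**What to change.** In Section 8, state which family experience items or scales are asked at both enrolment and 6 months. For those, replace the post-only bivariate test with a linear model of the 6-month score on study arm and the same family's enrolment score, using enrolment surveys completed before navigation starts. Give an interval that accounts for clinic with three clusters per arm, for example one based on clinic-level summaries with 4 degrees of freedom. Keep the intention-to-treat assignment. For items asked only at follow-up, keep the post-only comparison and report it descriptively. Treat PCP overall experience the same way only for items answered before training content was delivered.

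The cost is a few sentences and one covariate, with no new data collection. The protocol would also need a stated rule for families with a 6-month score but no enrolment score, such as a missing-baseline indicator, so that they do not drop out of the comparison.

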## 2) Objectives

Autism Access Link for Early Referral and Treatment [ALERT], the intervention proposed in this application, is a novel state-wide referral and case management platform that PCPs can activate to ensure that a child with suspected Autism Spectrum Disorder (ASD) receives all necessary ASD diagnosis and treatment resources in a single referral, radically simplifying a complex diagnostic and treatment process. We hypothesize that Autism ALERT will have strong acceptability and high rates of use among primary care providers as well as among diverse low-income patients of children at risk for ASD, and that we will see higher rates of child ASD educational evaluations within six months, and shorter time between referral and ASD treatment,.

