## 4) Study Design

We propose a pilot clustered interventional trial with two arms. Clinics in the intervention arm receive Autism ALERT plus an ASD screening intervention (START Autism), and clinics in the comparison intervention (control) arm receive only START Autism (no Autism ALERT). As this is a pilot trial, primary outcomes of interest are feasibility and acceptability. We will additionally assess mechanism of outcome, preliminary efficacy, and protocol fidelity. Feasibility and acceptability will be assessed in intervention clinics. Mechanism of action and preliminary efficacy will be assessed by comparing intervention to control clinics. Fidelity is assessed in both arms. We will pilot test Autism ALERT in 6 safety-net primary care clinics in Oregon: 3 clinics will serve as intervention clinics, receiving both Autism ALERT and START Autism, and 3 clinics will serve as controls receiving START Autism only. Study arm will be assigned via coin-flip randomization of clinics, stratified for size and urbanicity, by a statistician who is not otherwise part of the study team.

In 2023 we received new funding from CareOregon to expand the project. As a result, this pilot study will be expanded to all of Portland-metro area. It will no longer include a control arm. Participants will be recruited off of Autism clinic waiting lists in the PDX metro area, and will be enrolled into the study to receive family navigation services from our partners at Help Me Grow.

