## 5) Study Population

### a) Number of Subjects

The three subject groups include clinics, child/parent dyads, and providers. We seek to enroll 7 safety net primary care practices. 70 child/parent dyads will participate in this study (20–baseline condition, 25–intervention, 25–control). We estimate that 30 providers will participate in this study (15–intervention; 15–control). The number of participants per site will depend on the size of the participating clinics.

Per the expansion to all of Portland-metro area, we estimate that there will be around 300 children enrolled in the next 3 years.

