We will compare efficacy outcomes in the Autism ALERT group to the baseline and control groups, using bivariate analyses and Kaplan-Meier curves for time to treatment variables. Estimated effect sizes for the subsequent R01 will be measured using Cohen's d. To test engagement of target mechanisms, we will assess whether efficacy outcomes differed by mechanistic outcome (e.g., whether parental stress was associated with time to treatment), using bivariate or limited multivariable models. We will also assess whether outcomes differ according to family demographic characteristics, both overall and by study arm, to test variability in intervention effects. Secondary and exploratory efficacy outcomes from ecWeb and Medicaid claims will be analyzed in the same framework.

Fidelity outcomes include both structural measures (e.g., receipt of program components) and procedural measures (e.g., quality of delivery of these components). We will use descriptive

statistics to assess delivery of the START Autism ± Autism ALERT training curriculum components. We will also use descriptive statistics to calculate navigator fidelity to the protocol, using the Navigator Fidelity Checklists. Checklists will also be cross-checked with recorded calls to assure accurate documentation. We will use descriptive statistics to characterize PCP use of the Autism ALERT website. To understand how Autism ALERT and START Autism altered PCP screening and referral behaviors, we will assess rate of ASD screening and EI/ECSE referral in both study arms in the baseline condition, and 3-and 6-months after initiation of START Autism ±Autism ALERT. As an exploratory analysis, we will assess whether racial/ethnic or language differences in PCP screening are present, and whether they vary by study arm or by PCP/clinic characteristics.

Our goals in this pilot study are to assess the feasibility and acceptability of the intervention and analysis, develop hypotheses regarding mechanism of action, and to provide context for defining meaningful differences and otherwise inform R01 power calculations. We intentionally have not powered to detect statistically significant differences. However, estimates will provide preliminary evidence of intervention effects, generate effect size estimates, and will help refine analytic strategy, efficacy hypotheses, and sample size estimates for a larger study.

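### Clinics are assigned to arms, but the methods named for the ALERT-versus-control comparisons make no allowance for clinic, so precision is overstated if the ICC is above 0

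*Protocol*

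**What the plan says.** Section 4 (Study Design) describes the pilot this way: "We propose a pilot clustered interventional trial with two arms". On allocation it says "Study arm will be assigned via coin-flip randomization of clinics, stratified for size and urbanicity", with three clinics in each arm. It also says "Mechanism of action and preliminary efficacy will be assessed by comparing intervention to control clinics".

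Section 8 (Data Analysis) then names the methods for the between-arm comparisons:

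- Efficacy: "We will compare efficacy outcomes in the Autism ALERT group to the baseline and control groups, using bivariate analyses and Kaplan-Meier curves", the curves being for time to treatment. Cohen's d supplies the effect sizes for the R01.
- Family experience after the intervention: bivariate analyses by intention to treat.
- PCP experience: bivariate testing between arms.

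Clinic enters Section 8 only as a descriptor: whether navigator activities differ by site, and whether screening disparities vary with PCP or clinic characteristics. No clinic-level analysis, random effect, GEE, robust variance, ICC or design effect is named. Section 8 disclaims power, but intends the estimates as preliminary evidence of effect and as input to the sample size of a larger study.

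Section 5(a) gives the numbers: "70 child/parent dyads will participate in this study" (20 baseline, 25 intervention, 25 control) and "We estimate that 30 providers will participate in this study" (15 per arm). It also says "We seek to enroll 7 safety net primary care practices", whereas Sections 4, 5(b) and 5(e) say six. Section 5(d) describes administrator payment at six sites plus one more.

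**The concern.** Families and PCPs from one clinic share its staff, patient mix and local services, so their outcomes may be correlated. When clinics are assigned to arms, that shared component does not cancel between arms. A t-test, chi-squared test, log-rank test or standard interval for d run on individuals treats 25 families per arm as 25 independent pieces of information. Its p-values are then too small and its intervals too narrow.

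Two things are at stake: the preliminary evidence of effect, and the apparent precision of the effect sizes passed to the R01. Lack of power does not settle the matter, because the validity of an interval or p-value is separate from power. The protocol sets no alpha and no efficacy decision rule, so the harm is limited to these secondary contrasts and the R01 inputs.

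**Working it through.** The protocol states no ICC, design effect or power, so there is no figure of its own to reproduce. The totals agree: 20 + 25 + 25 = 70 dyads and 15 + 15 = 30 providers.

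**Inputs.** From Section 4: three clinics per arm. From Section 5(a): 25 families and 15 PCPs per arm. Assumed: ICC of 0 to 0.20; near-equal clinic sizes of 9, 8, 8 families and 5, 5, 5 PCPs.

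**Standard error.** With outcome variance 1, clinic sizes n_k and arm total N:

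Var(arm mean) = ICC × Σn_k²/N² + (1 − ICC)/N

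The naive value is 1/N. For families, Σn_k² = 81 + 64 + 64 = 209. At ICC 0.05:

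0.05 × 209/625 + 0.95/25 = 0.05472; 0.05472/0.04 = 1.368; √1.368 = 1.17.

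So 25 families carry the information of 25/1.368 = 18.3 independent ones. For PCPs the factor is √(1 + 4 × ICC).

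**Coverage.** 100,000 simulated null trials per setting. For normal outcomes, a pooled t interval on individuals was set against a t interval on clinic means. For the proportion reached by six months (assumed 50%, no earlier censoring), a Wald interval on 25 versus 25 was set against a t interval on clinic proportions with 4 df. The spread of d comes from 40,000 trials per ICC with true d assumed 0.5.

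**Half-width of a 95% interval for a standardised difference.** Naive: t on 48 df, 2.011 × √(2/25) = 2.011 × 0.2828 = 0.569. Clinic level: t on 4 df, multiplier 2.776.

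| ALERT versus control, assumed ICC | 0 | 0.01 | 0.05 | 0.10 | 0.20 |
|---|---|---|---|---|---|
| Families: true/naive SE | 1.00 | 1.04 | 1.17 | 1.32 | 1.57 |
| Families: naive coverage, % | 95.0 | 94.2 | 90.4 | 86.0 | 77.8 |
| PCPs: true/naive SE | 1.00 | 1.02 | 1.10 | 1.18 | 1.34 |
| PCPs: naive coverage, % | 95.0 | 94.6 | 92.6 | 90.2 | 84.8 |
| Families, 7 clinics split 4:3 (assumed): true/naive SE | 1.00 | 1.03 | 1.15 | 1.28 | 1.50 |
| Six-month proportion: naive coverage, % | 93.3 | 92.7 | 88.1 | 83.2 | 74.5 |
| Six-month proportion: clinic-level coverage, % | 95.1 | 95.1 | 94.8 | 94.7 | 94.4 |
| SD of estimated d | 0.29 | 0.30 | 0.35 | 0.39 | 0.47 |
| Half-width, clustering alone (naive 0.57) | 0.57 | 0.59 | 0.67 | 0.75 | 0.89 |
| Half-width, clinic level on 4 df | 0.79 | 0.81 | 0.92 | 1.03 | 1.23 |

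For families, the t interval on clinic means covers 94.8 to 95.1% throughout. The mean of d stays at 0.51 to 0.52, so its location is little affected. The last row includes a factor of 2.776/2.011 = 1.38 that is due to few degrees of freedom and is present even at ICC 0. In the six-month row, the shortfall at ICC 0 (93.3%) belongs to the Wald interval at this sample size; only the fall from there is clustering.

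**Unequal clinics.** Section 5(a) expects numbers per site to follow clinic size. With an illustrative 15, 6, 4 split, the naive type I error at a nominal 5% is 10.9, 16.9 and 27.6% at ICC 0.05, 0.10 and 0.20. For 9, 8, 8 it is 9.3, 13.9 and 22.5%.

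**Why ALERT versus baseline is left out.** The protocol does not say which clinics supply the 20 baseline families. With clinic shares p_k and q_k:

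Var = ICC × Σ(p_k − q_k)² + (1 − ICC)(1/25 + 1/20), against a naive 0.09.

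At ICC 0.05, 0.10 and 0.20 the true/naive SE ratio is:

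- 0.975, 0.95, 0.90 if they come from the same three clinics (7, 7, 6);
- 1.02, 1.04, 1.08 if they are spread evenly over all six;
- 1.15, 1.28, 1.51 if they come from three other clinics.

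The direction therefore depends on a fact the protocol does not give.

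**The case against.** **The unit of analysis is not stated.** A t-test on clinic means is also bivariate, and Section 4 speaks of comparing clinics. An SAP, not shown, could add an adjustment. This is why the point is conditional. But the reference to clinics identifies the arms rather than the unit of analysis, and Cohen's d and Kaplan-Meier curves are naturally family-level. The protocol has itself chosen methods, none of which is described as fitting its unit of assignment.

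**Section 8 promises no confidence intervals.** True. A plotted Kaplan-Meier curve is description, and d is a point estimate. However, bivariate analyses normally yield p-values, PCP experience is expressly tested, and an effect size passed on for planning needs a statement of precision.

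**The consequence is small.** Feasibility and acceptability are primary and are assessed within intervention clinics. Power is disclaimed, and the contrasts are imprecise either way: ±0.79 SD at ICC 0 on 4 df. No figure in the protocol supports an ICC above 0.01, where coverage is still 94.2%. All of this stands and limits the weight of the point, but it does not make the named analysis valid at larger ICCs.

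**Strata and layout.** Stratification by size and urbanicity may absorb some between-clinic variance, in which case an unstratified t on clinics minus 2 df is at worst conservative. Section 8 does not carry the strata into the analysis either. The layout is idealised: Section 5(e) says control enrolment is lagging, and Section 6 counts 41 pediatricians. Neither reverses the result.

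**Conclusion.** The concern holds, with a limited reach. Applied to families or PCPs as independent units, the methods Section 8 names overstate the precision of the ALERT-versus-control contrasts whenever the ICC is above 0. Over assumed ICCs of 0.01 to 0.20, the standard error is understated by a factor of 1.04 to 1.57 for families and 1.02 to 1.34 for PCPs. Nominal 95% coverage falls to between 94.2 and 77.8% for families and between 94.6 and 84.8% for PCPs. At ICC 0.01 the effect is small. These figures rest on three clinics per arm and near-equal clinic sizes; unequal sizes make the fault worse, and seven clinics change it little (1.15 instead of 1.17 at ICC 0.05).

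The point does not extend to the value of d itself, ALERT versus baseline, pre-post change (where stable clinic effects drop out), feasibility and acceptability, or the uncontrolled expansion. It should be corrected, but it does not threaten the pilot's primary aims.

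**What to change.** In Section 8:

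- State that ALERT-versus-control contrasts in families and PCPs account for clinic. Use either clinic-level summaries compared by t on the number of clinics minus 2 df, or a mixed model or GEE with clinic as cluster and a small-sample correction. Uncorrected GEE or robust errors would also be too narrow with three clinics per arm.
- For time to treatment, keep the Kaplan-Meier curves as description and compare clinic-level Kaplan-Meier summaries, such as the proportion reached by six months. That is the horizon Section 2 uses for evaluations: "higher rates of child ASD educational evaluations within six months". With about eight families per clinic (25/3), early censoring would make these summaries fragile.
- For baseline comparisons, state where the 20 baseline families come from and keep clinic in the model.
- Report each effect size with a clinic-adjusted interval, as an estimate rather than a 5% test.
- Size the R01 over a range of ICCs. Six clinics cannot pin one down: an observed 0.05 has an F-based 95% interval (4 and 44 df, mean clinic size 25/3) of about −0.07 to 0.57.
- Reconcile six and seven clinics, since the count sets the degrees of freedom.

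The cost is analysis wording only, because each family's and PCP's clinic is known from recruitment. The downside is wider intervals, on 4 df with six clinics or 5 df with seven.
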